### **3.3.2 Control – Standard of care**

The existing Ministry of Health and Child Care programme of direct HIVST distribution in the community through community health workers (CHW) will be the standard of care in the study.

### **3.3.3 HIV risk self-assessment tool**

Previous work has indicated that males in this community have a low level of perception of their risk of HIV infection. [41, 50] To address this, a tool will be developed that will allow study participants to make a self-assessment of their level of risk. Information on how to use the tool will be provided to all recipients of HIVST kits including the primary distributors as part of the kit insert. They can use this tool multiple times during the study period as their risk profile may change over this time. All SMS messages will be free, and no identifying data will be collected by the study team. After submission of an SMS users will be prompted by an automated interactive system to provide a numerical response to a series of behavioural risk questions. The questions will be the same as those used in the national PrEP screening tool. Based on the responses they will receive an automated message indicating whether they have a high level of risk and if so recommending that they consider PrEP initiation.

### **3.3.4 Study Helpline**

A study helpline with a toll-free number will be established which will provide the key point of contact between the participants and the study team. In addition to the structured contact with the participants as outlined below all participants will be able to contact the helpline with any questions or concerns about the study, the interpretation of their results, for support and counselling related to HIVST or their engagement with the healthcare clinics or for any other reason. The helpline will be staffed within working hours with a messaging/call-back service available out of these times.

### **3.3.5 HIVST kits**

In this study we will use the WHO approved OraQuick oral fluid test kits (OraQuick ADVANCE® Rapid HIV-1/2 Antibody Test, OraSure Technologies, Inc.)

### **3.3.6 HIVST packaging and kit inserts**

Study specific packaging will be created for each HIVST kit into which the original kit with packaging from the manufacturer will be inserted. A sticker on each box will contain the following information:

- A unique 6-digit identifier for the kit
- A set of tick-boxes on which the clinic staff will record the outcome of the engagement with the clinic
- A kit insert sheet within each box will contain the following:
  - A copy of the informed consent form
  - Details of accessing SMS-based HIV risk self-assessment tool
  - Contact details for the study helpline
  - Details of the study procedures including the renumerations paid for successful kit distribution and engagement of recipients with the primary care clinics

- Detailed instructions on the use and interpretation of the HIVST kit

Individual HIVST kits will be placed in a larger box with its own unique identifier. Four kits will be provided in these boxes for the primary distributors and three for the secondary distributors. The study team will keep a record of the unique identifiers of the kits packaged in each box to enable the kit distribution process to be tracked.

### 3.3.7 Strategies to improve adherence

Follow-up calls from the study helpline will be the main strategy to support participants through HIV self-testing and engagement with HIV care. These calls will be made at monthly intervals following the initiation of ART or commencement of PrEP.

### 3.3.8 Process Evaluation

The process evaluation will be primarily conducted in one urban and one rural site. A trained Shona-speaking qualitative researcher will lead the evaluation, alongside a team of trained research assistants and peer researchers (men from the target population acting as local community advisors and research assistants). Qualitative data will be thematically coded and analysed in NVivo 12. The performance evaluation consists of three stages, with all data collected informing the final evaluation stage. (Fig 3)

[figure not shown]

Figure 3 Framework for the Performance Evaluation

First, a **pre-intervention context analysis** will be conducted to understand the context within which the intervention will be implemented, and thus to improve the fit between context and approach (months 7-12). Workshops with men who represent the target group (n=2), healthcare providers (n=2) and project implementers (n=2) will provide feedback on and help refine the intervention, further develop the evaluation logic model, and identify local resources that can support the intervention. Focus group discussions with men (n=4) will explore the structures, attitudes and practices surrounding men's social networks, to inform intervention design to maximize its reach to PrEP-eligible individuals in terms of HIVST distribution, uptake and clinic attendance. Finally, participant observations will generate notes about all planning processes. All these inputs will be used to map, and design trial adaptations to account for, barriers and facilitators for implementation and sustainment.

Second, accountability mechanisms will generate **real-time feedback during implementation** to support the PI's in strengthening of intervention practices (months 13-42). Focus group discussions (n=4) and interviews (n=12) with implementers will capture barriers and

facilitators to implementation success, what is and is not working and any unintended consequences. A designated helpline and mailboxes for anonymous feedback will be available at all study sites to allow helpline and other staff provide qualitative insights into how the intervention is progressing. Focusing on the two sites subject to qualitative investigation, participant observations of intervention implementation and home and community visits will help monitor progress, as well as interactions in peer networks and between men and shopkeepers distributing HIVSTs. All this will be triangulated with real-time quantitative data on enrolment and progress of men through the intervention.

Third, the **post-trial process evaluation** will examine “what works in which circumstances for whom” (months 43-48). Through interviews (n=24) and focus group discussions (n=8) with a mix of stakeholders, including men reached through the intervention (in combination with intra-trial data), we will explore contextual factors and social network mechanisms shaping experiences of, and engagement with, intervention activities along the HIV prevention cascade (see Figure 5). This will include examining the ‘what’ (social network structures and processes), the ‘how’ (implementation processes), ‘where’ (spatiality, location, community/cultural/ political/religious context), ‘when’ (timing, momentum, cyclical, flow, speed, duration, frequency), and ‘who’ (people and organisations, interpersonal relations, social networks and norms) that influence HIVST distribution and PrEP uptake. Finally, 20 men will be invited to photographically capture ‘stories of change’ through the Photovoice method. [51]. The men will be invited to write captions to their photos, and to select photographs representing ‘significant changes’ (good or bad). These photographs will guide subsequent interviews, which will also seek to understand how the men’s social networks affect the changes they report by visualizing their personal networks and using them as a tool for discussion.[52, 53]. Further details of the Photovoice procedures are given below.

As a token of appreciation for participating in process evaluation activities, workshop participants will be given USD\$10 at the end of the activity, individual qualitative interview participants will be given 2 bars of laundry soap, focus group discussion participants will be given 2 bars of laundry soap, and Photovoice participants will be given a t-shirt and USD\$10.

### **Photovoice guidelines**

#### Justification for Photovoice

Photovoice is a research method that qualitatively captures the lived experiences of participants in ways that words alone, produced through interview interactions, cannot capture. In this project it will be used as a participatory evaluation method. Photovoice provides participants with time to reflect on key barriers and facilitators to success of an intervention, and to photographically capture and articulate their perspectives. Although the photographs, and accompanying written reflections about their meanings, constitute important data in their own right, the reflection that takes place during the Photovoice exercise, can be explored further in interviews. Photovoice therefore both triangulates and strengthens interview methods.

#### Process (step-by-step)

1. 20 men aged 18 and above who have participated in the intervention will be invited to participate in this exercise. They will be recruited from two different intervention clusters.

A key criterion for selection is their representativeness and interest to participate in Photovoice.

2. A three-hour photography workshop will be arranged at a central location (e.g., community hall, school classroom) of each cluster to cover the following:
  - a. Aims and objectives of the exercise
  - b. What we are interested in (theme: men's experiences of the peer network intervention). The men will be asked to focus their photography and reflections around the following three questions:
    - i. 'How did the intervention affect you?'
    - ii. 'What are the most significant accomplishments of the intervention?'
    - iii. 'What aspects of the intervention were not particularly successful?'
  - c. The practicalities of using a camera and take good pictures.
  - d. Ethical dilemmas with photography in public areas – this will include an explanation and dialogue about the consent forms. The men will be encouraged to think of scenarios where taking a photograph may not be appropriate and could cause discomfort to those photographed. These scenarios will be discussed and the men will be told that if they want to share a story and they are unsure about whether it may be inappropriate to take the photo, or if they do not get an opportunity to take a representative photo, they can draw the scenario instead and describe their drawing(s). The men will be discouraged from taking photos of people who may be identifiable.
3. The men will be given two weeks to take photos answering the above questions. After the two weeks the cameras shall be collected for development of the photos with two copies being printed of each photo.
4. After development of the photographs, the men will be gathered in a second workshop and asked, echoing the aims and objectives of this exercise, to pick six of their favourite photos that depict one or more of the following:
  - a. Two photos capturing the most significant accomplishments of the intervention.
  - b. Two photos depicting something that helped make the intervention a success or failure.
  - c. Two photos that depicts something that enabled or prevented men from engaging with the intervention.Again, if the men want to share a story and scenario they did not capture with the camera, they were encouraged to draw the scenario. The men will be invited to pick six photos they are happy to share with the research team, who might make the photos available in the public domain, and will be asked to sign the photograph release consent form.
5. The men will be encouraged to write short essays to each of the six photos with the following guidelines:
  - i. 'I want to share this photo/drawing because...'
  - ii. 'What's the real story this photo/drawing tells?'
  - iii. 'How does this story relate to your life and/or the lives of other men in your community?'

#### Training, facilitation, accountability and ethics oversight

1. *Participant training* – Photovoice participants will be thoroughly trained on the purpose of the exercise, use of cameras, the ethics of taking pictures in public for research purposes,

and in the process for obtaining informed consent from the subjects in photographs. In terms of the ethics of picture taking, we will introduce the participants to a variety of strategies to overcome key ethical dilemmas. These include: i) draw a situation that cannot be captured photographically for ethical research; ii) use themselves, and each other, to stage a scenario that fictitiously depict a situation they would like to capture photographically; iii) think creatively about how they tell a story photographically without people appearing in the pictures; iv) refrain from taking pictures of people and places that can be recognized on the images.

2. *Facilitator training* – The person facilitating the Photovoice exercise has previous experience of implementing a Photovoice project, but will receive further training from the study investigators, who has written academic articles and book chapters on the use of Photovoice in health research.
3. *Community oversight* – Local community leadership will be involved in the selection of men, and consulted on the use of Photovoice in their communities. The advice we receive from the local community, and their inputs on what constitutes ethical and unethical picture-taking, will shape the trainings listed above. Village headmen/women will be included in parts of the training (as well as in the initial consultations) and requested to oversee the process. In practice, they may delegate day-to-day oversight and monitoring responsibility to VCHWs or other responsible community members. If/when significant problems arise, these can be referred to the headman/woman to resolve.
4. *Fieldwork team level oversight*: We will appoint one of the field supervisors to review the photographs and consent forms coming in on a weekly basis to make sure they conform to the ethical requirements; and to obtain details from the headmen/women of any cases referred to them to resolve. This person will then prepare monthly reports summarizing their findings.
5. *Investigator level oversight*: Photovoice participants will be given access to the project's 24-hour phone line so that they can report complaints immediately to one of the PIs ([name]) who will arrange to have such complaints investigated and acted upon as necessary. [name] will review the supervisor's monthly reports, provide instructions on any remedial action that might be necessary in the field, and make decisions on the ethical suitability (or not) of related photos/drawings for use in the research.

### 3.3.9 Modelling Study

PopART-IBM is an individual-based model originally developed and successfully used to generate long-term projections of impact that have been used in estimating the cost-effectiveness of the HPTN 071 (PopART) trial. [54] It is computationally efficient, capable of simulating 50 years of an HIV epidemic in a population of 100,000 individuals, using a weekly timestep, on a standard laptop in under a minute. [54] Thus, it can explore hundreds of thousands of parameter combinations on a standard computer cluster. Work comparing the calibrated output of PopART-IBM in Zambia with phylogenetic analysis from the same community provides validation of the simulated sexual transmission network in a sub-Saharan African setting. [55]

The model will be modified to explicitly include an HIV testing channel corresponding to self-testing and parameterize this using age-specific uptake rates over time in men collected as secondary outcome data. Initialisation of PrEP will be added as part of the self-testing process, as shown in the model schematic, with initialization additionally contingent on overcoming

the barriers associated with every step in the HIV Prevention Cascade. Using an inference framework,[54] multiple simulations consistent with the trajectory will be used to take parametric uncertainty into account; uncertainty resulting from stochasticity of the model can also be taken into account. Impact will be calculated relative to a simulated counterfactual in which the intervention was not introduced, and will also be calculated for the HIV self-testing component alone, using approaches to evaluation that we have previously successfully applied. [56, 57] The measures of impact will be HIV infections and deaths averted, as well as DALYs averted for the cost-effectiveness analysis, under the assumption that uptake of HIVST and PrEP are maintained over time. Using the multiple simulations, we can generate uncertainty bounds arising from stochastic and parametric uncertainty.

### **3.3.10 Cost Effectiveness analysis**

The modelling framework will be used to undertake a formal cost-effectiveness analysis. This analysis will use the actual costs and observed outcomes and will project the stream of benefits that could accrue to the men and their partners and the indirect population-level benefits.

## **3.4 Outcomes**

**The primary outcome** of the trial will be the proportion of men initiating PrEP out of all men aged 18 and over.

**Secondary outcomes will include:** i) the proportion of men self-testing for HIV over the period of the intervention out of all men aged 18 and over. and ii) the proportion of screened men adhering to PrEP or ART six months after initiation, measured by laboratory analysis of dry blood spots, out of all men initiating PrEP or ART after receiving an HIVST kit.

The qualitative performance evaluation will inform work to combine several quantitative data sources to evaluate how the intervention spread through social networks, and how network position and structure affected trial outcomes. We will combine information on intended and actual HIVST recipients with the existing Manicaland census data to measure what proportion of PrEP/ART eligible men were reached by our intervention. We will assess the level of network saturation achieved by the distribution process [16], and whether our approach reached individuals at higher risk of HIV acquisition as the recruitment process advanced – a key aim of the respondent driven sampling (RDS) methods on which our peer recruitment methods are based. Using entity resolution algorithms and hand-checking, we will identify linkages across distribution chains, and from this build network graphs of connections between men in the study areas. We will use these graphs to describe the structure of local male peer networks and statistically evaluate how characteristics of distributors and their social contacts influenced network distribution process and subsequent engagement with care. We will also evaluate whether intervention success differed across study clusters based on cluster-level network structures (e.g., density, clustering, age, and risk homophily) as well as by non-network characteristics (e.g., urbanicity, economy). Finally, once wider geographic distribution occurs in the second trial phase, we will evaluate whether distribution chains overlap and if greater geographical distribution affects study outcomes. We expect that our work will explain variation in outcomes and detail the contextual factors to consider when replicating or taking this intervention to scale. [33] We also expect to develop light-touch tools for use by implementors pre- and during implementation of such interventions, which can guide localization of this socially mediated design.

Through the modelling study we will generate population-level estimates of the incremental impact over three and ten years of: (i) the introduction of HIVST through male social networks and associated PrEP uptake; (ii) the introduction of HIVST alone.

From the Cost-effectiveness analysis, summary measures of benefit will include infections averted, reductions in lifetime-risk for men, deaths averted, and DALYs averted compared to the simulated counterfactual. Adjustments will be made to model the costs as they would be in a 'routine' application, removing any elements that are exclusively required by the evaluation. All uncertainties in the epidemiology, cost, outcome, and potential for future compensatory changes would be reflected in the model.

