- iv. After seven days the helpdesk will contact the distributor and the intended recipients to ascertain whether kits have been received and used, to collect behavioural HIV risk data for the recipients and encourage attendance at a healthcare facility for a confirmatory test. HIVST recipients will be invited to complete the informed consent over the telephone and be enrolled in the study. Follow-up calls will be made to these individuals if necessary. Recipients will be encouraged to consider becoming distributors and advised on the location of community facilities (shops, pharmacies, hairdressers etc.) from where they can obtain the HIVST packs for distribution. This method of HIVST distribution through community-based hubs has been proven to be successful in studies in other Sub-Saharan African settings. [48] A small renumeration of \$1 per peer will be transferred electronically to the initial distributor for each kit successfully distributed. Successful distribution to peers is defined as the peer having received the HIVST and has been successfully contacted by the helpline to confirm receipt of the HIVST but does not have to use the HIVST or agree to enrol in the study as a distributor. Names and cell numbers will be collected for intended recipients by the study team and held confidentially.

- v. If the recipient chooses to become a distributor they will go to the facility and the owner will check using a real-time database that they have not already received a pack of kits for distribution. If they pass this screening, they will be given a pack of three HIVST kits for within cluster distribution, again A small renumeration will be paid to the facility owner for each pack of kits given out.
- vi. After seven days the helpdesk will contact the second level recipients and steps iv) and v) will be repeated until all kits allocated to a particular community have been distributed.
- vii. When participants attend a clinic for confirmatory testing, they will return the HIV test kit packaging with the unique label and based on their self-reported HIVST result (unreactive/reactive) be screened for PrEP or ART. The outcome of the screening will be recorded in a tick-box on the label and the packaging deposited in a secure box at the clinic from where it will be collected by the study team.

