## 5 Methods: Data collection, management, and analysis

### 5.1 Data collection methods

There will be three modes of data collection used in this study

- i) Direct data collection by fieldworkers for the recruitment of the primary distributors.

- ii) Telephone-based data collection by the central helpline staff for all follow-up data and enrolment of peers
- iii) Central data entry of information data on kit packaging labels

Data collection will be carried out by trained research assistants on password protected tablets and smartphones which are tracked via an asset register. These devices will be collected from the Data Management team at the start of the day and returned at the end of the day to be stored in a locked room. Data will be entered using Open Data Kit installed on tablets and smartphones and will be transferred to the electronic database on a daily basis. Following confirmation of successful data transfer, records will be deleted from the smartphones and tablets at the end of each day, in order to minimise the amount of data stored on these devices.

All data will be entered into a central database and used for study monitoring and analysis.

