## **5.3 Statistical methods for analysing primary and secondary outcomes**

For the test of the intervention effect on the primary and secondary outcomes will be conducted using the intent-to-treat (ITT) analysis for all men randomized at the community level. We will define our intent to treat population as those clusters who were randomized to intervention and control groups. We will use generalized linear models with Poisson distribution, log link function and robust error terms, adjusting for community-level clustering through random effects.

Analysis of baseline data will be carried out once recruitment has completed in all clusters. Final analyses will begin following field data and all associated data cleaning and quality control procedures. No interim analyses will be conducted.

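### Secondary outcome (i) counts any HIV self-test in both arms, but every stated data source records study kits only, so the between-arm test compares study-kit use with a control figure that omits the control condition's own tests

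*Protocol*

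**What the plan says.** Section 3.4 gives secondary outcome (i) as "the proportion of men self-testing for HIV over the period of the intervention out of all men aged 18 and over". The numerator is not limited to study kits and the denominator is not limited to enrolled men.

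Section 5.3 begins "For the test of the intervention effect on the primary and secondary outcomes" and prescribes an intention-to-treat analysis of men in all randomised communities, using a log-link Poisson model with random effects for clustering.

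Section 3.3.2 states that the Ministry's existing programme of "direct HIVST distribution in the community through community health workers (CHW) will be the standard of care in the study". Control men are thus offered the very behaviour that outcome (i) counts.

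On ascertainment, section 3.3.1 step iv reads: "After seven days the helpdesk will contact the distributor and the intended recipients to ascertain whether kits have been received and used". Steps vii and viii add the return of labelled study-kit packaging at clinics. Section 5.1 says "There will be three modes of data collection used in this study". The first is "Direct data collection by fieldworkers for the recruitment of the primary distributors". The second is helpline follow-up and the enrolment of peers, and the third is data entry from study-kit labels.

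**The concern.** The outcome is wider than the means of measuring it, and the mismatch depends on arm. A man who uses a study kit has a route into the data. A man who uses a Ministry kit has none, in either arm. In the intervention arm the loss is partial, because most users are expected to use study kits. In the control arm it removes the whole of the standard-of-care activity.

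The question for this outcome is whether peer distribution raises self-testing above what health workers already achieve. A comparison that omits the health workers' tests cannot answer it, and a small p-value would follow from the recording alone. An analysis plan cannot repair this, because it cannot analyse control-arm data that no source collects.

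**Working it through.** **Inputs, all from Protocol 3.6 unless stated.** 3,591 men; 22 + 22 clusters; at most 90 kits per intervention cluster; 70% of kits reach men in the cluster; 80% of those men use the kit; 33% eligible for PrEP; 43% of those initiate; intra-cluster correlation 0.1. Past self-test use in men is under 6% (2.1.2). Control self-testing during the trial is not given.

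**The plan's own figure.** 90 × 0.70 × 0.80 × 0.33 × 0.43 = 7.15 initiators per cluster; × 22 = 157; 157.3/1,795.5 = 8.8%. This matches 3.6, so the inputs are being used as the plan intends. No power is stated for outcome (i).

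**Study-kit use implied by the same inputs.** Men per cluster: 3,591/44 = 81.6. Men reached: 90 × 0.70 = 63. Users: 63 × 0.80 = 50.4. Share: 50.4/81.6 = 61.8%.

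**Who has a recording route**

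| Self-test | Helpline use call | Returned label | Distributor recruitment |
|---|---|---|---|
| Study kit, intervention cluster | yes | yes | primary distributors only |
| Study kit leaked to a control cluster | possible | possible | no |
| Ministry kit, intervention cluster | no | no | no |
| Ministry kit, control cluster | no | no | no |

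Apart from leakage, men with no route number about 1,795.5 + 22 × (81.6 − 63) = 1,795.5 + 409.5 = 2,205, or 2,205/3,591 = 61%.

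**Bias in the difference.** Let c be the true control rate. Assume that intervention men who do not use a study kit also self-test at rate c, and that the recorded control figure is about zero.
- True intervention rate: 0.618 + 0.382c
- True difference: 0.618 + 0.382c − c = 0.618 − 0.618c
- Recorded difference: 0.618
- Excess: 0.618c

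| Assumed c | True difference (points) | Excess (points) | True ratio (0.618 + 0.382c)/c |
|---|---|---|---|
| 3% | 59.9 | 1.9 | 21.0 |
| 6% | 58.0 | 3.7 | 10.7 |
| 10% | 55.6 | 6.2 | 6.6 |
| 20% | 49.4 | 12.4 | 3.5 |

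**Ratio as recorded.** With no control events a log-link model has no finite rate ratio. If leaked study kits gave a recorded control figure of, say, 1% (an assumption), the recorded ratio would be 61.8/1 = 62, against the true values in the last column.

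**What the test would do under no effect.** Suppose study kits merely replaced Ministry kits, with equal true self-testing in both arms, recorded only in the intervention arm. The design effect is 1 + 80 × 0.1 = 9, so the effective size is 22 × 81/9 = 198 men per arm. On that basis a nominal two-sided 5% test (level assumed; normal approximation) would reject about 52% of the time at a true rate of 2%, 94% at 6% and over 99% at 10%.

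**The case against.** **Other sources may exist.** The protocol says that it will draw on the long-running surveillance programme (2.1.1), which is described as ongoing (2.3). Section 5.2 mentions survey data, and 5.3 mentions a baseline analysis once recruitment is complete in every cluster. This stands to the extent that a common source looks feasible. None of these passages commits to a round after distribution that asks control men about self-testing, and 3.4 uses census data only to measure how many eligible men the intervention reached.

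**Zero is not guaranteed.** A reader might infer a contrast of 62% against zero by construction, with an infinite ratio. The documents do not support that. Phase two lets initial distributors give kits to men living elsewhere in the same site, with follow-up as before (3.3.1). Section 3.6 also assumes that 30% of kits, 27 × 22 = 594, do not reach men in the cluster. Some could be used and scored in control clusters. Such a count would measure contamination, though, not standard-of-care testing. The 62% is itself only a planning value at the kit maximum.

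**The difference is not wrong by the full control rate.** A reader might also subtract all of c. Nothing says that the Ministry programme is withdrawn from intervention clusters, so unrecorded tests there offset part of the error. That is why the excess is 0.618c under the stated assumption.

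**The effect would be large anyway.** On the planning figures a true difference of 49 to 60 points remains over the assumed range. This stands: if uptake goes to plan, the harm is to the size of the effect more than to its direction. The protection disappears if uptake falls well short.

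**The impact model.** Section 3.3.9 takes self-testing uptake from secondary outcome data, and a reader might infer that a false control zero enters the model. The text does not say so; the model's counterfactual is simulated.

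Section 5.1 names no control-arm route for PrEP initiation either. That is a separate question and is not argued here.

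**Conclusion.** The point holds as a mismatch between the outcome, the data sources and the planned test, all three of which the protocol fixes. Ministry-kit self-tests count under 3.4 and form the control condition under 3.3.2, yet no stated source records them in either arm. The planned contrast is study-kit use against a near-zero control figure that could reflect only leakage.

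The recorded difference would be too large by about 2 to 12 points for an assumed control rate of 3% to 20%. The recorded rate ratio would be grossly inflated, or not estimable if no control event is recorded. These sizes rest on four assumptions: the 90-kit planning figures, negligible leakage, equal Ministry-kit use among control men and intervention men who do not use a study kit, and a control rate that the protocol does not give. That ascertainment depends on arm rests on none of them.

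**What to change.** Amend 3.4, 5.1 and 5.3 together, in one of two ways.

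1. **Keep the between-arm test**, on condition that 5.1 names one source that ascertains self-testing in the same way in both arms and 3.4 counts any self-test, whoever supplied the kit. The self-test-use item of the ongoing surveillance is a candidate if a round follows distribution. The protocol does not show that one does.
2. **Otherwise redefine outcome (i)** as the proportion of men aged 18 and over in intervention clusters who use a study kit. Report it descriptively with a cluster-adjusted confidence interval, and remove it from the between-arm test in 5.3.

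The second option costs wording only; the price is that one secondary comparison becomes descriptive. The first preserves the randomised comparison but depends on a data source that the protocol does not yet commit to.
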